8.2. Secondary Efficacy Endpoint

8.2.1. Key Secondary Efficacy Endpoint

The key secondary endpoint is RRT incidence during the period Day 1 (after first treatment) to Day 28, inclusive. Should a patient die or withdraw from the study during this period without recording RRT incidence, he or she will be counted as having not required RRT.

Analysis of this key secondary endpoint will be performed for the ITT Combined Set and PP Day 1– 7 Combined Set.

The optimal recAP dose will be formally compared with placebo using a logistic regression model with treatment group and site as explanatory variables, if a statistically significant result is obtained from the combination test analysis of the primary endpoint. Otherwise the results will be reported as exploratory analyses only. In the event that there are issues with the model (e.g. quasi-complete separation of data points) the reason will be investigated and if needed, site will be removed from the model. In this case, it will be documented as a deviation from the protocol in order to avoid a questionable validity of the model fit.

This endpoint will additionally be summarized for all four treatment groups using counts and percentages. The odds ratio and associated 95% confidence interval from the comparisons of the optimal recAP dose versus Placebo will also be presented. The counts and percentages will also be presented for ITT Part 1 Interim Set and ITT Part 2 Set separately.

The analysis of this key secondary endpoint will be repeated excluding patients who died or withdrew from the study prior to completion of this 28 Day period. If a statistically significant result is obtained from the combination test analysis of the primary endpoint and the key secondary endpoint, the optimal recAP dose will be formally compared with placebo using a logistic regression model with treatment group and site as explanatory variables.

The analysis of RRT incidence for the ITT Combined Set will also be presented for the supportive factor analysis as described in section 8.1.5 for the primary endpoint.

RRT data will be presented in a listing.

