### **3 Investigational Plan**

#### **3.1 Study Design**

This is a randomized, double-blind, placebo-controlled, 4-arm, parallel-group, proof-of-concept, and dose-finding adaptive Phase 2a/2b study.

Approximately 100 sites will participate in the study; approximately 75 in the European Union and approximately 25 in the United States and Canada. Participating sites will be required to adhere to the Surviving Sepsis Campaign 2012 (Delinger et al 2013) and KDIGO® (Kidney Disease: Improving Global Outcomes) Clinical Practice Guideline for AKI recommendations (KDIGO Acute Kidney Working Group 2012).

A minimum of 290 patients with SA-AKI will be enrolled in the study. The study involves 2 parts (Part 1, Part 2) with an interim analysis between the parts, with continued recruitment during this interim analysis. Of the 290 planned patients, at least 120 patients will enroll in Part 1 and 170 patients will enroll in Part 2 with an estimated 50 patients during the interim analysis. Patients enrolled during Part 1 and interim analysis will be randomly assigned to receive, by 1-hour IV infusion, either placebo (Part 1; n1 = 30) or one of 3 different doses of recAP (Part 1; n1 = 30 in each dosing arm; i.e., 0.4 mg/kg [250 U/kg], or 0.8 mg/kg [500 U/kg], or 1.6 mg/kg [1000 U/kg]) using a 1:1:1:1 allocation ratio. Patients will receive study drug by 1-hour IV infusion once daily for 3 days (Days 1, 2, and 3). The interim analysis on the primary endpoint will be performed on all the data collected after the 120th patient of Part 1 has completed the Day 7 visit of the study to select the dose to be administered in Part 2. The dose chosen will be the optimal dose of recAP on the primary endpoint in Part 1, provided there are no safety issues with that dose as judged by the data monitoring committee (DMC). In Part 2, patients will be randomly assigned to receive, by 1-

[figure not shown]
hour IV infusion, either placebo ( $n_2 = 85$ ) or the dose of recAP ( $n_2 = 85$ ) selected during the interim analysis. Patients recruited during the interim analysis period to the dose selected in Part 2 will form part of the Part 2 populations, but those recruited to the doses that are not selected will be included in the Part 1 population.

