4.1. Sample Size

A sample size of $n_1 = 30$ patients per treatment group in Part 1 with an additional $n_2 = 85$ patients recruited to each of the optimal recAP dose and placebo treatment groups in Part 2 (for a total sample size of $n = 290$ patients) is planned. Recruitment will continue during the interim analysis, so the total number of patients will exceed 290. Custom programmed simulations were performed using SAS[®] Version 9.2 (SAS Institute, Inc, Cary, North Carolina) to determine power and type I error rate of the chosen sample size and design under a number of different dose response scenarios. Each scenario assumed a standard deviation of 49 mL/min for the primary endpoint (area under the time-corrected endogenous creatinine clearance curve from Day 1 to Day 7 [AUC₁₋₇]) with an assumed response of 60 mL/min for the placebo group, and between 60 mL/min (no treatment effect) and 79 mL/min (strong treatment effect) for the recAP dose groups.

Fifty-thousand simulations were performed to show that the 1-sided type I error rate is 2.4% (and hence is well controlled at the 1-sided 2.5% significance level). The power was defined as the probability of rejecting the null hypothesis (of no difference between treatment groups) when 1 or more recAP dose groups have an effective treatment effect, defined as a response of 69.5 mL/min. This was investigated across 7 scenarios with 10 000 simulations performed for each. In the most realistic scenarios (with strong treatment effects, i.e., responses of 79 mL/min for the medium and high recAP dose groups and a varying response of between 60 mL/min and 79 mL/min for the low-dose group) the chosen design achieved power of between 79% and 86%. This dropped to 66% to 67% for other scenarios where only the high recAP dose group had a strong treatment effect.

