8.3. Other Efficacy Endpoints

Composite Endpoints

Patients that meet, or do not meet at least 1 of the following criteria will be summarized by counts and percentages for each composite endpoint:

Composite Endpoint 1:

1. Received RRT (prior to Day 28 [inclusive]) or
2. Died (prior to Day 28 [inclusive])

Composite Endpoint 2:

1. eGFR < 60 mL/min (at Day 60, estimated by the CKD-EPI formula based on serum creatinine) or
2. Dialysis dependency (up to Day 60) or
3. Died (prior to Day 60)

Composite Endpoint 3:

1. eGFR < 60 mL/min (at Day 90, estimated by the CKD-EPI formula based on serum creatinine) or
2. Dialysis dependency (up to Day 90) or
3. Hospitalized for a new episode of AKI (prior to Day 90) or
4. Died (prior to Day 90)

Exploratory analysis of each composite endpoint will be undertaken for the comparison of the optimal recAP dose and placebo using a logistic regression model with treatment group and site as explanatory variables. The odds ratio and associated 95% confidence interval from the comparisons of the optimal recAP dose versus Placebo will be presented together with the p-value for this comparison.

Serology

Serology is assessed by IgG, IgE, and total immunoglobulin at Baseline, Day 14 and Day 28.

The observed values and change from baseline for IgG, IgE, and total immunoglobulin will be calculated by visit and summarized with descriptive statistics.

All Serology data will be listed.

Anti-Drug Antibody Data

All anti-drug antibody data will be listed.

Quality of Life

Quality of Life is assessed by the EQ-5D questionnaire at Baseline, ICU/Intermediate care discharge, and Day 90.

The questionnaire assesses 5 dimensions: mobility, self-care, usual activities, pain/discomfort and anxiety/depression. Each dimension has 5 response options (no problems, slight problems, moderate problems, severe problems, and extreme problems) that reflect increasing levels of difficulty. The patient will be asked to indicate his/her current health state by selecting the most appropriate level in each of the 5 dimensions.

The questionnaire also includes a visual analogue scale, where the patient will be asked to rate current health status on a scale of 0-100, with 0 being the worst imaginable health state.

The EQ-5D responses from each dimension will be summarized with counts and percentages by treatment group and visit.

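### The formal RRT test may rest on a site-term logistic model that is biased at this site count or on a model without site, and no objective rule says which

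*SAP*

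**What the plan says.** If the primary combination test is significant, SAP 8.2.1 has the selected dose "formally compared with placebo using a logistic regression model with treatment group and site as explanatory variables". Protocol 7.7.2 specifies the same model. On analysis sets, SAP 8.2.1 states: "Analysis of this key secondary endpoint will be performed for the ITT Combined Set and PP Day 1– 7 Combined Set". The repeat analysis that leaves out deaths and withdrawals uses the same model.

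SAP 8.2.1 also has a fallback. It names quasi-complete separation as an example of a model problem and continues: "the reason will be investigated and if needed, site will be removed from the model". Removing site is then to be recorded as a protocol deviation. The section gives no threshold, no time point and no statement on who decides or whether that person is blinded.

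The three exploratory composite endpoints in SAP 8.3 are compared "using a logistic regression model with treatment group and site as explanatory variables", without a fallback.

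On site numbers, Protocol 3.1 says: "Approximately 100 sites will participate in the study". Neither document gives a rule for pooling small sites, or an assumed RRT rate or power for this endpoint.

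**The concern.** A logistic model with one term per site estimates many nuisance parameters from very few patients each. Ordinary maximum likelihood then pushes the treatment odds ratio away from 1 and makes the Wald test too liberal. Conditional or Mantel-Haenszel methods avoid this because they do not estimate the site terms.

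The fallback does not settle the matter. Separation occurs as soon as one site has only RRT patients or none. If that is practically certain, the condition is practically always met, and a judgement decides which of two models gives the reported p-value. RRT incidence is the only formally tested endpoint after the primary, and Protocol 3.1.1 calls it relevant for Phase 3. An overstated odds ratio would feed directly into Phase 3 planning.

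**Working it through.** **Inputs from the documents.** Per arm 30 (Part 1) + 85 (Part 2) = 115, so 2 × 115 = 230 compared patients (SAP 4.1). About 100 planned sites, so 230 / 100 = 2.3 patients per planned site. Two-sided 5% level (SAP 4). Randomisation is stratified by site in permuted blocks of unstated size (SAP 4.2).

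**The plan's own figure.** The documents give none for RRT. As a check on the design inputs, simulating the AUC1-7 design gave power of 81.4%, 79.1% and 85.7% with the low dose at 60, 69.5 and 79 mL/min, against the stated 79-86%. One-sided type I error was 2.5% against the stated 2.4%.

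**Why separation is practically certain.** The model is logit P(RRT) = α(site) + β × treatment. A site with one patient always has all or no events. With an assumed 30% RRT rate, a site with two patients does so with probability 0.7² + 0.3² = 0.58, and one with three with probability 0.7³ + 0.3³ = 0.37. At least one such site occurred in every simulated trial, even with about 34 enrolling sites. These sites carry no information on β: in the 100-site null settings only about 105-170 of the 230 patients contributed.

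**Type I error.** 2,000 trials per setting with no treatment effect. Assumptions, not in the documents: placebo RRT 20 / 30 / 40%, site SD 0.5 on the logit scale, blocks of two within site. With 2,000 trials the Monte Carlo error at 8% is 1.96 × √(0.08 × 0.92 / 2000) = 1.2 points.

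| Planned sites, recruitment (mean enrolling) | ML with site terms | Conditional logistic by site | No site term | Either of ML with site or no site |
|---|---|---|---|---|
| 100, even (90) | 9.6 / 9.9 / 11.2% | 4.4 / 4.6 / 5.3% | 4.2 / 4.1 / 5.1% | 10.2 / 10.2 / 11.8% |
| 100, uneven (70) | 7.5 / 8.3 / 7.9% | 4.3 / 4.8 / 4.4% | 4.2 / 4.8 / 4.0% | 8.4 / 8.8 / 8.6% |
| 60, uneven (48) | 6.8 / 8.3 / 7.9% | 4.5 / 5.7 / 5.7% | 4.0 / 4.8 / 5.1% | 7.3 / 8.6 / 8.6% |
| 40, uneven (34) | 6.0 / 5.9 / 7.1% | 4.8 / 4.2 / 5.4% | 4.5 / 4.1 / 5.0% | 6.2 / 6.4 / 7.4% |

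The inflation does not depend on real site differences: with site SD 0, 100 sites and even recruitment it was 9.9%. Simple randomisation gave 7.0-9.0%. Likelihood-ratio tests were slightly worse than Wald tests.

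**Closer to the trial's allocation.** Four-arm schedule stratified by site, two codes dropped after Part 1, block size 4, placebo RRT 35%, site SD 0.5 (the last three assumed).

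| Planned sites | Type I error, ML with site terms | True OR 0.60 read as |
|---|---|---|
| 100 | 8.4% | 0.51 |
| 60 | 7.0% | 0.54 |
| 40 | 7.0% | 0.56 |

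In the same settings the site-stratified CMH test had type I error of 4.8-5.2%, and the Mantel-Haenszel odds ratio was 0.60-0.61. The model without site had 3.9-5.1%. Free choice between the two logistic models gave 7-9%.

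**Effect of the gate.** Suppose the AUC1-7 effect is real (power about 80%), RRT is unaffected and the two tests are independent. A false RRT claim then occurs in 0.80 × 5% = 4.0% of trials at the nominal level, and in 0.80 × 6% = 4.8% to 0.80 × 9% = 7.2% with the site-term model.

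**The case against.** The strongest reply is that the SAP already holds the remedy. If separation occurs in practically every trial, and separation is the named reason for removing site, the reported model would usually be treatment only, whose error is near nominal. That is correct. A reader might infer that the planned RRT p-value is anti-conservative as written; the documents do not support this, because the inflation applies only if the site model is kept or if the choice is made after seeing both results. The change history for SAP 3.0 even describes the removal of site as a plain rule. The operative text in SAP 8.2.1 nevertheless makes it a matter of judgement and labels it a protocol deviation.

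A reader might also infer that the model will be picked after the unblinded fit. The SAP does not say so. SAP 4.2 releases the codes once the database is final, and SAP 8.2.1 gives no timing, so this is possible but not planned. Sites with all or no events could be identified from pooled data without treatment codes.

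Two further readings go too far. About 100 is a planned site count for the whole trial, not the number of fitted terms; about 34-70 sites would enrol compared patients if 40-100 sites recruit unevenly. And the known result that one pair per site squares the odds ratio (0.60² = 0.36) is a limit that does not describe this design, where the simulated value is 0.51-0.56.

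Finally, this is a Phase 2a/2b trial, the test is gated, and the composites are exploratory. The reason given for Change 7 of Amendment 1 (Protocol 14.1.7.1) calls the study a learning trial that does not need strong type I error control. This lowers the severity. It does not excuse an overstated odds ratio on the endpoint meant to inform Phase 3.

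**Conclusion.** The point holds as an unresolved choice between two models. The model named in both documents, read as ordinary maximum likelihood with site terms, is biased at this site count. If kept, its two-sided type I error is about 6-9%, rising to about 11% with even recruitment over 100 sites, and it reads a true odds ratio of 0.60 as about 0.51-0.56. With no true effect its odds ratio is centred on 1. The model without site is near nominal. Nothing objective decides between them, and free choice gives about 7-9% false positives.

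These sizes rest on assumed RRT rates (20-40%), site variation, block sizes and recruitment patterns, none of which is in the documents. That ordinary maximum likelihood is meant is also an inference: no other form is named, and the separation example fits it. Severity: should-fix.

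**What to change.** In Protocol 7.7.2 and SAP 8.2.1, name one method for the formal RRT comparison and its repeat analysis: the Mantel-Haenszel odds ratio with a CMH test stratified by site, or conditional logistic regression with site as stratum. Delete the clause that lets site be removed. Show the unstratified odds ratio as a sensitivity result. Use the same method for the composites in SAP 8.3, for consistency only. This fits the SAP's existing practice: randomisation is stratified by site (4.2), as are the log-rank tests for time off ventilator (8.2.2.2) and ICU discharge (8.3).

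The cost is wording, one changed procedure and no patients. There is some power loss against the model without site, because sites with one arm or no outcome variation drop out. For CMH it is about 0-4 points at a true odds ratio of 0.60, and up to about 8 points in the least favourable setting simulated with site-stratified allocation and 100 sites. Conditional logistic regression lost more under simple randomisation, which this trial does not use (100 sites, uneven recruitment, true odds ratio 0.50): 44.0% against 56.5%.

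A smaller change would also work: keep the fallback but make it mandatory, with an objective trigger assessed on treatment-blind data. In practice that means reporting the model without site.

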8.2.2. Other Secondary Efficacy Endpoints

Unless stated otherwise all analysis on the other secondary endpoints will compare the optimal recAP with placebo and be based on the ITT Combined Set, i.e. include all patients randomized to those treatment groups during Part 1 and Part 2 of the study. All summary statistics, counts and percentages, and data listings will be based on the ITT Combined Set, displaying results for all four treatment groups and including all patients randomized during Part 1 or Part 2 of the study.

8.2.2.1. Renal

Volume of Urine, Serum Creatinine, BUN/Urea Clearance, Proteinuria

A summary table will present descriptive statistics for the following renal endpoints: volume of urine (daily from Day 1 to Day 7, inclusive, and on Day 14, 21 and 28 if reliable 6 hour urine collection is possible); Serum creatinine, proteinuria, blood urea nitrogen (BUN) and urea clearance (daily from Day 1 to Day 7, inclusive, and on Day 14, 21 and 28 and on Day 60 and 90 for serum creatinine and proteinuria).

Urine volume will be collected over a 6 hour period +/- 1 hour period, and converted to mL/hour by PPD Biostatistics. Urine output (mL/hour) will be calculated using the following formula:

$$\text{Urine output (mL/hour)} = \frac{\text{Urine output collected (mL)}}{(\text{Stop date / time of Urine Collection} - \text{Start date / time of Urine Collection, in hours})}$$

The calculated values per hour will be used in the tables and figures.

Urea clearance (mL/min) will be calculated by PPD Biostatistics using the following formula.

$$\frac{\text{Urine Urea Nitrogen (mg/dL)}}{\text{BUN (mg/dL)}} \times \frac{\text{Total urine volume collected (mL)}}{\text{Stop date/time} - \text{Start date/time of urine collection (min)}}$$

- The urine urea nitrogen (mg/dL) and BUN (mg/dL) assessed by the central laboratory will be used to determine the urea clearance.
- Per protocol, two blood samples are collected to evaluate the BUN, one at the beginning of the urine sample collection and the other at the end of the urine sample collection. The average of these two BUN measurements will be used in the formula above to assess the urea clearance. In case there is only one BUN sample available, then the BUN concentration from that one sample will be used in the formula.
- The number of minutes from the start date/time to the stop date/time of urine sample collection and the total urine volume (mL) will be derived from the Urine Volume eCRF page. If the urine volume is recorded as 0 mL, then the urea clearance will be 0 mL/min and will not be set to missing.

A time-course plot of serum creatinine, urine output and BUN/urea clearance by day will be presented separately.

All data for these endpoints will also be listed.

A summary table will present the descriptive statistics for the peak value of serum creatinine and the peak value of blood urea nitrogen (during the period Day 1 to Day 7, inclusive).

RRT

A summary table for RRT during the period Day 1 to Day 28 will be presented including the following endpoints: RRT-free days, total number of days on RRT, reasons for initiation of RRT, and reasons for stopping RRT.

An RRT-free day is a day on which a patient did not receive any form of RRT. Conversely, a day on RRT is defined as a day on which a patient received any form of RRT for any period of time on that day. For intermittent RRT, the following additional rules apply:

- Following conclusion of intermittent RRT, if the patient then has a period of six or more days before next initiation of any form of RRT, all (six or more) days in this intervening period are counted as RRT-free.
- Following conclusion of intermittent RRT, if the patient then has a period of five or less days before next initiation of any form of RRT, all (five or less) days in this intervening period are counted as RRT.

Table 8-1 Example of Derivation of RRT-Free Days and Days on RRT

On intermittent RRT	Off RRT	On RRT	RRT-free days	Days on RRT
Day 2 to Day 4 inclusive	Day 5 to Day 9 inclusive	Day 10 to Day 15 inclusive	0	14
Day 2 to Day 4 inclusive	Day 5 to Day 10 inclusive	Day 11 to Day 15 inclusive	6	8
Note: all instances of Day refer to study day				

RRT-free days from Day 1 to Day 28 will be summarized by descriptive statistics. The total number of days on RRT from Day 1 to Day 28 will also be summarized by descriptive statistics.

Reasons for initiation of RRT and reasons for stopping RRT will be summarized by counts and percentages. A patient can have more than one reason for initiation, but will only be counted once under each reason in the table if the patient reported that reason multiple times. The same approach will be applied for patients who report more than one reason for stopping.

Exploratory analysis of the total number of days on RRT will be undertaken for the comparison of the optimal recAP dose and placebo using an ANOVA with treatment and site as explanatory variables. The least square means for each treatment and the difference in least squares means between the treatment groups will also be presented along with the associated 95% CI and p-value. If a subject withdrew from study or died while still on RRT treatment before Day 28, then duration of RRT (ie, number of days on RRT) will be calculated as from RRT start date up to Day 28 (ie calculating with the "remaining days up to Day 28). For the calculation of total number of days on RRT, any missing RRT stop days will be set to either the day before the next RRT start date if more than one RRT record or to Day 28 if the patient has no further RRT records.

All RRT data will be listed.

Kidney function

The reference eGFR will be estimated by the CKD-EPI formula based on the reference serum creatinine value recorded on the AKI Diagnosis page of the eCRF for each patient. The reference serum creatinine value is recorded on the eCRF using the following order of preference:

1. Lowest value within 3 months of the hospital admission; if not available then:
2. Value at hospital admission; if not available then:
3. Value ICU/Intermediate care admission; if not available then:
4. Lowest value between 3 and 12 months prior to hospital admission

Baseline serum creatinine from the laboratory data will not be included in the calculation of reference eGFR.

Kidney function will be assessed at Baseline, Day 14, 21 and 28 by measured creatinine clearance. Baseline kidney function will only be measured by standardized creatinine clearance, however for Day 14, 21 and 28 summaries if creatinine clearance is not available then kidney function as assessed by eGFR (estimated by the CKD-EPI formula based on serum creatinine) will be used.. Kidney function will also be assessed at Day 60 and Day 90 by eGFR. Sustained loss of Kidney function, defined by eGFR < 60 mL/min, will be assessed at Day 60 and Day 90. The analyses of kidney function and sustained loss of kidney function at each timepoint will exclude any patients who die prior to the timepoint. Any other missing assessments (including early withdrawals) at Day 60 or Day 90 will be imputed by LOCF where possible, missing Day 14, 21 and 28 values will not be imputed and will be treated as missing. A summary table will present descriptive statistics for the reference kidney function and the kidney function at Baseline and at Days 14, 21, 28, 60 and 90 along with counts and percentages of patients with loss of sustained kidney function at Day 60 and Day 90. Descriptive statistics will also be presented for the change from baseline creatinine clearance value at Day 14, Day 21, Day 28, Day 60, and Day 90.

The absolute difference between placebo and each of the treatment groups will also be presented at each time point. Summaries for Day 60 and 90 will be repeated with and without the LOCF imputation of missing values applied.

All kidney function data will be listed.

Dialysis Dependency

Incidence of dialysis dependency will be assessed at Day 60 and Day 90. Patients who die or withdraw from the study prior to Day 60 or Day 90, respectively, without recording incidence of chronic dialysis will be counted as not being dialysis dependent. A summary table will present the counts and percentages of patients who are dialysis dependent at Day 60 and Day 90. Percentages for each timepoint are calculated based on the number of patients that were assessed including those who died or withdrew prior to timepoint.

All data on dialysis dependency will be listed.

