## 7.3 Other Secondary Endpoints

### 7.3.1 Renal

- Renal endpoints include the following:
- Volume of urine (daily from Day 1 to Day 7, inclusive, and on subsequent visit days if reliable urine collection is possible)
- Serum creatinine and BUN (daily from Day 1 to Day 7, inclusive, and on subsequent visit days if reliable urine collection is possible)
- BUN clearance (daily from Day 1 to Day 7, inclusive, and on subsequent visit days if reliable urine collection is possible)
- Peak value of serum creatinine and BUN (during the period Day 1 to Day 7, inclusive)
- RRT-free days (during the period Day 1 to Day 28 excluding patients who died or withdrew from the study prior to the end of this period), i.e., 28 days minus the number of days a patient is on RRT during this period. An RRT-free day is defined as a day on

which a patient did not receive any form of RRT. Conversely, a day on RRT is defined as a day on which a patient received any form of RRT for any period of time on that day.

For intermittent RRT, the following additional rules apply:

- a. Following conclusion of intermittent RRT, if the patient then has a period of six or more days before next initiation of any form of RRT, all (six or more) days in this intervening period are counted as RRT-free
  - b. Following conclusion of intermittent RRT, if the patient then has a period of five or less days before next initiation of any form of RRT, all (five or less) days in this intervening period are counted as on RRT
- Total number of days on RRT (during the period Day 1 to Day 28, inclusive). A day on RRT is defined as a day on which a patient did receive any form of RRT for any period of time on that day.
  - Reasons for initiation of RRT (during the period Day 1 to Day 28, inclusive)
  - Kidney function at Day 28 as assessed by measured creatinine clearance if available, otherwise as assessed by eGFR (estimated by the CKD-EPI formula based on serum creatinine). Patients who die prior to Day 28 will be excluded from this endpoint, with any other missing assessments (including early withdrawals) imputed using LOCF.
  - Kidney function at Day 60 and Day 90 as assessed by eGFR (estimated by the CKD-EPI formula based on serum creatinine). Patients who die prior to Day 60 or Day 90, respectively, will be excluded from this endpoint, with any other missing assessments (including early withdrawals) imputed using LOCF.

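### SAP Table 8-1 prints 0 and 6 RRT-free days where the SAP's own Day 1 to Day 28 definition gives 14 and 20

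*SAP*

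**What the plan says.** SAP 8.2.2.1 (Renal, under RRT) defines the unit of the endpoint: "An RRT-free day is a day on which a patient did not receive any form of RRT". For gaps that follow intermittent RRT it adds two rules. In a gap of at least six days, "all (six or more) days in this intervening period are counted as RRT-free"; in a shorter gap, "all (five or less) days in this intervening period are counted as RRT". The reporting sentence directly after the table fixes the period: "RRT-free days from Day 1 to Day 28 will be summarized by descriptive statistics".

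Protocol 7.3.1 has the same gap rules and states the calculation outright: "28 days minus the number of days a patient is on RRT during this period". The SAP does not repeat that subtraction for RRT-free days, in either 3.2.3 or 8.2.2.1. It does use the equivalent subtraction for ventilator-free days in 8.2.2.2.

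Table 8-1, "Example of Derivation of RRT-Free Days and Days on RRT", gives two cases. Both have intermittent RRT on "Day 2 to Day 4 inclusive". In the first, the patient is off RRT on "Day 5 to Day 9 inclusive" and on RRT again for Days 10–15. In the second, the patient is off RRT for Days 5–10 and on again for Days 11–15. The printed results are 0 RRT-free days with 14 on RRT, and 6 RRT-free days with 8 on RRT. The only note to the table says that days are study days.

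**The concern.** Over a 28-day period, RRT-free days and days on RRT should sum to 28. In both rows of the table they sum to 14. The table's title and column heading carry the endpoint's own name, and the SAP change history (version 1.4) describes this part of 8.2.2.1 as detail on how RRT-free days are calculated. A programmer or validator could therefore reasonably treat the rows as test cases.

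Code written to reproduce 0 and 6 would drop RRT-free days before the first and after the last day of RRT. The endpoint would be understated, and the two RRT columns in the summary table would no longer be complementary.

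**Working it through.** **Inputs.** Period Days 1–28 (SAP 8.2.2.1), 28 days. Formula from Protocol 7.3.1: free = 28 − on. Gap rule: five days or fewer count as on RRT, six or more count as free. Episodes are as in Table 8-1. Neither row lists RRT on Day 1 or Days 16–28, and the printed totals of 14 and 8 leave no room for any.

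**Days on RRT.**
- Row 1: Days 2–4 (3) + five-day gap counted as RRT (5) + Days 10–15 (6) = 14. This matches the table.
- Row 2: Days 2–4 (3) + Days 11–15 (5) = 8, with the six-day gap counted as free. This matches the table.

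**Reproducing the printed RRT-free days.** The values 0 and 6 appear if counting is limited to the span from the first to the last day of RRT, Days 2–15, which is 14 days: 14 − 14 = 0 and 14 − 8 = 6.

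**Applying the stated definition.** Over Days 1–28:
- Row 1: 28 − 14 = 14 (Day 1 and Days 16–28).
- Row 2: 28 − 8 = 20 (Day 1, Days 5–10 and Days 16–28).

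**Other windows**, to see whether a different stated or implied period explains the table:

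| Window | Length (days) | Row 1 free | Row 2 free | Matches the table? |
|---|---|---|---|---|
| Days 1–28 | 28 | 14 | 20 | No |
| Days 2–28 | 27 | 13 | 19 | No |
| Days 1–15 | 15 | 1 | 7 | No |
| Days 2–15 | 14 | 0 | 6 | Yes |

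Of the four windows, only Days 2–15 reproduces the table. The shortfall is the same in both rows: 14 − 0 = 14 and 20 − 6 = 14, that is, Day 1 (1 day) plus Days 16–28 (13 days).

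**The case against.** The best defence is that the table was meant only to illustrate the gap rule. It follows directly after the two rules, and the two gaps are five and six days, exactly where the rule switches. Over the 14 days displayed, every figure is right: 0 + 14 = 14 and 6 + 8 = 14. This is a plausible account of how the table came about, and it suggests a missing label more than a slip in arithmetic. It does not remove the problem, because neither the title, the column heading nor the note limits the count to Days 2–15.

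Two stronger readings are tempting, and the documents do not support them.

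- A reader might infer that the example is the SAP's only numerical specification of the endpoint. It is not. The text before and after the table gives the definition, the gap thresholds and the Day 1 to Day 28 period, which together determine 14 and 20. The SAP is based on Protocol Version 3.0, which has the subtraction formula, and the SAP's list of changes from the planned analysis does not withdraw it.
- A reader might infer that any patient with a single RRT episode would be scored zero free days, however long the episode. The table contains no such case. The inference also requires the programmer to ignore the adjoining text. The same logic gives no value for a patient who never had RRT, so the misreading would probably surface early. Nothing in the documents says that code is checked against this table.

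**Conclusion.** The point holds as an internal contradiction. Table 8-1 disagrees with the text around it and with Protocol 7.3.1, and under the stated definition its RRT-free column should read 14 and 20. This rests on the two example patients having no RRT on Day 1 or Days 16–28, which the table's own totals imply.

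The 14-day shortfall belongs to these two constructed patients. It is not an estimate of bias in the trial's summary. Any effect would depend on the code having followed the example instead of the text, which the documents do not show.

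The reach is narrow. The SAP only summarizes RRT-free days descriptively. The exploratory ANOVA uses total days on RRT, which the example derives correctly. AUC1-7 and RRT incidence do not use this derivation, and the SAP's supportive factor analyses are confined to those two endpoints. Protocol 7.6 does list RRT-free days among its subgroup endpoints, so the correct derivation still matters if those summaries are produced. This is a minor correction, worth making because it is cheap.

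**What to change.** 1. In Table 8-1, change the RRT-free column to 14 and 20, with a note that the patients have no other RRT in Days 1–28. Alternatively, keep 0 and 6 and label the column as covering Days 2–15 only.
2. In SAP 8.2.2.1, state that RRT-free days equal 28 minus days on RRT over Days 1–28. Days on RRT should be derived by the gap rules and by that section's rule that carries RRT forward to Day 28 for patients who die or withdraw while on it.
3. In the same sentence, say how days after death or withdrawal are counted for patients who were off RRT at that point. Protocol 7.3.1 paired its formula with the exclusion of patients who died or withdrew, and SAP version 3.0 removed that exclusion. A bare subtraction would therefore credit a patient who dies off RRT with free days after death. The SAP has a status-based rule for this in ventilator-free days but none for RRT-free days.

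The first two changes cost two numbers (or a label) and one sentence. The third needs a short decision on the counting rule. None requires new data.
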